6.1.3. Laboratory Tests

All tests listed in Table 2 below will be performed according to the Schedule of Visits and Assessments ([Section 1.3](#)), unless otherwise noted. No food restrictions are required for the collection of specimens. In addition, laboratory safety tests may be performed at various unscheduled time points, if deemed necessary by the Investigator. Laboratory samples will be sent to the central lab. Refer to the most current Central Laboratory Manual for collection, processing, ship, and report receipt instructions.

Table 2: Laboratory Tests

Hematology	Serum Chemistry

• Hemoglobin• Hematocrit• Total and differential leukocyte count• Red blood cell count with indices and morphology• Platelet count	
• Blood Urea Nitrogen• Bilirubin (total and direct)• Alkaline phosphatase• Aspartate aminotransferase• Alanine aminotransferase• Albumin• Sodium• Potassium• Chloride• Glucose• Creatinine

Table 2: Laboratory Tests (Continued)

Urinalysis	Additional Tests

• pH• Specific gravity• Protein*• Glucose• Ketones• Bilirubin• Blood*• Nitrite*• Urobilinogen• Leukocyte esterase*	
• Urine pregnancy test• (for females of childbearing potential only)• Serum pregnancy test (hCG)**• Pharmacokinetic (PK) assessments• Malassezia Test***

* If urinalysis is positive for protein, blood, nitrite, and/or leukocyte esterase, a microscopic examination (for red blood cells, white blood cells, bacteria, casts, and epithelial cells) will be performed.

** At Screening only

*** Samples collected for Cohort 1 Group 2 subjects only and may be used for *Malassezia* testing.

6.1.4. Patient Health Questionnaire depression scale (PHQ-8)

The 8 item PHQ-8 Assessment (see [Appendix 1](#)) will be completed by adult subjects according to the Schedule of Visits and Assessments ([Section 1.3](#)).

A subject with a PHQ-8 score of '15' or above should be referred promptly to a mental health care professional and, if currently applying investigational product, consideration should be given to discontinuation from investigational product.

Subjects with PHQ-8 >10 at Screening (Cohort 2 only) or Day 1 will be excluded from the study.

PHQ-8 score is the sum of the responses for the 8 questions.

Five severity categories of depression are defined as follows:

- None – Minimal depression (0 to 4)
- Mild depression (5 to 9)
- Moderate depression (10 to 14)
- Moderately severe depression (15 to 19)
- Severe depression (20 to 24)

6.1.5. Patient Health Questionnaire depression scale (Modified PHQ-A)

The 8 item Modified PHQ-A Assessment (see [Appendix 2](#)) will be completed by adolescent subjects (12-17 years old, inclusive) according to the Schedule of Visits and Assessments ([Section 1.3](#)).

A subject with a PHQ-A score of 15 or above should be referred promptly to a mental health care professional and, if currently applying IP, consideration be given to discontinuation from investigational product.

Subjects with PHQ-A >10 at Screening (Cohort 2 adolescents only) or Day 1 will be excluded from the study.

Modified PHQ-A score is the sum of the responses for the 8 questions.

Five severity categories of depression are defined as follows:

- None – Minimal depression (0 to 4)
- Mild depression (5 to 9)
- Moderate depression (10 to 14)
- Moderately severe depression (15 to 19)
- Severe depression (20 to 24)

6.1.6. Children's Depression Inventory 2

The CDI-2 Assessment will be performed according to the Schedule of Visits and Assessments ([Section 1.3](#)) for subjects 9 to 11 years old, inclusive.

The CDI-2 quantifies depressive symptomatology using reports from children/adolescents, teachers, and parents or caregivers. It is recommended for use in initial evaluation and is appropriate when there is a need for an assessment and robust description of a child's depressive symptoms.

This study will use the CDI Parent Report Form. An example of the Parent Report Form is presented in [Appendix 6](#).

A subject with a CDI-2 raw score of ≥ 21 for females and ≥ 22 for males should be referred to a mental health professional.

A subject with a CDI-2 raw score of ≥ 32 should be immediately referred to a mental health professional, and Investigators in consultation with the mental health professional should consider interruption or discontinuation of the IP.

6.1.7. Columbia-Suicide Severity Rating Scale (C-SSRS)

C-SSRS Assessments will be performed according to the Schedule of Visits and Assessments ([Section 1.3](#)) for subjects 12 years old and older.

On all visits, the Since Last Visit version ([Appendix 4](#)) will be used for Cohort 1. Cohort 2 will use the Baseline-Screening version ([Appendix 3](#)) for Screening and Since Last Visit version ([Appendix 4](#)) for Day 1 and all remaining visits.

If a subject has a score greater than 0 in suicidal ideation at Screening (Cohort 2 only) or Day 1, this is important and may indicate the need for mental health intervention. The investigator should not enroll the subject in the study.

Any score greater than 0 in the suicidal ideation score is important and may indicate the need for mental health intervention and consideration be given to discontinuation from IP. This should result in prompt referral to a mental health professional and/or possibly the emergency room. The Medical Monitor should be contacted.

The trained administrator will conduct the C-SSRS. The C-SSRS administrator will be trained via the C-SSRS training video. A training certificate for the administer(s) will be on file in the trial master file at the site.

An Investigator must review the completed C-SSRS. A qualified mental health care provider must be available, immediately if needed, to refer the subject for further evaluation.

6.1.8. Local Tolerability Assessments

The Investigator Local Tolerability Assessment will be an overall assessment of local tolerability.

Application site reactions will be graded at the timepoints outlined in the Schedule of Visits and Assessments ([Section 1.3](#)). Irritation reactions are graded using the scale detailed in the following section ([Berger 1982](#)). **Reactions at the site of product application, which may occur post-Baseline, should be differentiated from the preexisting inflammation associated with the subject's seborrheic dermatitis.**

The Investigator assessments will be conducted by the Investigator prior to any investigational product application in the study site.

Dermal Response

- 0 = no evidence of irritation
- 1 = minimal erythema, barely perceptible
- 2 = definite erythema, readily visible; minimal edema or minimal papular response
- 3 = erythema and papules
- 4 = definite edema
- 5 = erythema, edema and papules
- 6 = vesicular eruption
- 7 = strong reaction spreading beyond application site

Other Effects

- A = slight glazed appearance
- B = marked glazing
- C = glazing with peeling and cracking
- D = glazing with fissures
- E = film of dried serous exudates
- F = small petechial erosions and/or scabs
- G = no other effects

The Subject Local Tolerability Assessment will be an overall assessment of local tolerability and performed at the timepoints outlined in the Schedule of Visits and Assessments ([Section 1.3](#)).

This assessment will be administered on Day 1 at the site 10 to 15 minutes after IP application at the study site. Assessments at the study site during Weeks 4, 12, 24, 36 and 52 will be a recall assessment of the subject's experience 10-15 minutes after IP application since the last study visit.

Grade	Sensation Following Investigational Product Application
0 (none)	No sensation
1 (mild)	Slight warm, tingling sensation; not really bothersome
2 (moderate)	Definite warm, tingling sensation that is somewhat bothersome
3 (severe)	Hot, tingling/stinging sensation that has caused definite discomfort

6.1.9. Pigmentation Assessment

The Investigator will assess for pigmentation in areas affected previously and/or currently by seborrheic dermatitis at the timepoints outlined in the Schedule of Visits and Assessments ([Section 1.3](#)).

Hypopigmentation and hyperpigmentation will be scored individually using a 0 – 3 scale: ‘0’ for none, ‘1’ for mild, ‘2’ for moderate, and ‘3’ for severe.

6.1.10. Adverse Events

Adverse events (AEs) will be collected beginning at informed consent and assessed at the following visits and throughout the study according to the Schedule of Visits and Assessments ([Section 1.3](#)).

AE collection will end upon completion of study participation for subjects who complete or early terminate from the study without any new or ongoing AEs. Subjects with new or ongoing related AEs upon study completion or early termination will be followed for up to one month after the end of treatment until the symptoms or clinically significant abnormal laboratory test value(s) return to normal or acceptable levels, as judged by the Investigator.

Treatment emergent AEs will be followed in the clinic for up to one month at the Investigator's discretion until resolved or otherwise judged as clinically stable.

Refer to [Section 6.6](#) for further details on Adverse Events.

6.1.11. Phone Visits

Phone visits at Weeks 18, 30 and 44 will be conducted for all subjects to review any adverse event or concomitant medication changes.

6.1.12. Pharmacokinetic Assessment

An optional pharmacokinetic sample will be collected during the Week 4 visit for Cohort 2 subjects between 12 – 16 years of age. Adolescent subjects must give assent and the parent/legal guardian give consent for the PK collection. Collect the PK sample while the subject is having safety laboratory samples drawn. Ensure the PK sample is not drawn on the area where IP is applied.

6.1.13. *Malassezia* Testing

Samples will be collected at select sites by an Investigator from treated and untreated areas of Cohort 1 Group 2 subjects by swabbing the skin surface according to the Schedule of Visits and Assessments (Section 1.3). The collected samples may be used for *Malassezia* testing. Samples should be collected from the same areas as those collected during the ARQ-154-116 Baseline visit. Refer to the *Malassezia* sample collection instruction manual for details.

6.2. Efficacy Evaluations

6.2.1. Investigator Global Assessment (IGA)

Investigator's Global Assessments ('whole body' and 'intertriginous area') will be performed at the study visits according to the Schedule of Visits and Assessments (Section 1.3). The IGA should be completed prior to any other physician assessments.

The IGA is a static evaluation of qualitative overall seborrheic dermatitis severity. This global assessment scale is an ordinal scale with five severity grades (reported only in integers of 0 to 4). Each grade is defined by a distinct and clinically relevant morphologic description that minimizes inter-observer variability.

Every effort must be made for the same Evaluator to complete the IGA for the subject at every study visit.

Investigator Global Assessment of Disease (IGA)

Score	Description
0	Completely clear: [REDACTED]
1	Almost clear: [REDACTED]
2	Mild: [REDACTED]
3	Moderate: [REDACTED]
4	Severe: [REDACTED]

6.2.2. Overall Assessment of Erythema

Overall Assessment of Erythema will be performed at the timepoints outlined in the Schedule of Visits and Assessments (Section 1.3).

Overall Assessment of Erythema is a static qualitative evaluation, involving an ordinal scale with 4 severity grades (reported only in integers of 0 to 3). Each grade is defined by a distinct and clinically relevant morphologic description that minimizes inter-observer variability.

Every effort must be made for the same Evaluator to complete the Overall Assessment of Erythema for the subject at every study visit.

Overall Assessment of Erythema

Symptom	Score	Description
Erythema	0	None: [REDACTED]
	1	Mild: [REDACTED]
	2	Moderate: [REDACTED]
	3	Severe: [REDACTED]

6.2.3. Overall Assessment of Scaling

Overall Assessment of Scaling will be performed at the timepoints outlined in the Schedule of Visits and Assessments ([Section 1.3](#)).

Overall Assessment of Scaling are static qualitative evaluations, involving an ordinal scale with 4 severity grades (reported only in integers of 0 to 3). Each grade is defined by a distinct and clinically relevant morphologic description that minimizes inter-observer variability.

Every effort must be made for the same Evaluator to complete the Overall Assessment of Scaling for the subject at every study visit.

Overall Assessment of Scaling

Symptom	Score	Description
Scaling	0	None: [REDACTED]
	1	Mild: [REDACTED]
	2	Moderate: [REDACTED]
	3	Severe: [REDACTED]

6.2.4. Body Surface Area (BSA)

BSA Assessments will be performed at the timepoints outlined in the Schedule of Visits and Assessments ([Section 1.3](#)).

The BSA affected by seborrheic dermatitis will be determined by the subject's hand method, where the subject's hand (including fingers) surface area is assumed to equal 1% of body surface area (BSA).

[figure not shown]
6.2.5. Worst Itch Numerical Rating Scale (WI-NRS)

Given that itch is an important symptom of seborrheic dermatitis, a WI-NRS assessment is included in the present study. A responder analysis will be performed to evaluate achievement of a 4-point reduction of WI-NRS, which has been described as optimal for demonstrating a level of clinically meaningful improvement in itch severity in other skin conditions, including other forms of eczema ([Yosipovitch 2019](#)) and psoriasis ([Kimbball 2016](#)).

WI-NRS Assessments will be performed at the timepoints outlined in the Schedule of Visits and Assessments ([Section 1.3](#)).

The WI-NRS has been developed as a simple, single item to assess the patient-reported severity of this symptom at its highest intensity during the previous 24-hour period. (Naegeli 2015).

The WI-NRS will be determined by asking the subject's assessment of worst itch over the past 24 hours. The scale is from '0 to 10' ("no itch" to "worst imaginable itch"). Subjects will complete the WI-NRS pruritus assessment.

6.2.6. Scalpdex

The Scalpdex will be completed at the timepoints outlined in the Schedule of Visits and Assessments ([Section 1.3](#)).

Subjects will complete the Scalpdex. See [Appendix 5](#) for the Scalpdex.

6.2.7. Dermal Imaging

Medical photography will be performed at selected sites at Day 1, Weeks 4, 12, 24, 36 and 52 using Canfield photography equipment. Photography should be focused on single lesions or specific body sections (e.g. forehead). Body or half body photos should only be taken if necessary. All efforts will be made to de-identify the subjects. Subjects who are unwilling to participate in the medical photography will be allowed to opt out of this procedure and documented on the informed consent. Refer to the current Photography Manual for instructions regarding photography.

6.3. Final Study Visit

The approximate final study visit will occur at the end of Week 52 of overall involvement in the study. The procedures performed during this visit is described in the Schedule of Visits and Assessments ([Section 1.3](#)). A 7-day scheduling window is allowed for this visit. Adverse events will be recorded as reported by the subject or followed to resolution as outlined in [Section 6.6.5](#).

6.4. Early Termination Visit

If a subject is withdrawn from the study, a termination visit will be scheduled. This visit should include the procedures and assessments that would be performed at the Week 52 visit. It will be noted in the database which subjects have completed the study and which were early terminations.

6.5. Unscheduled Visit

Subjects that clear between scheduled visits should return for an unscheduled visit for the Investigator to confirm IGA score are considered 'clear' and subject will stop application of investigational product after Investigator confirmation. Subjects will call the site when seborrheic dermatitis returns prior to restarting application of investigational product. Unscheduled visits may also be necessary to repeat testing following abnormal laboratory

results, for follow-up of AEs, or for any other reason, as warranted in the judgment of the Investigator.

The following information will be collected for all subjects:

- AEs
- Concomitant medications/procedures

The following information will be collected for those subjects that had stopped study medication but are experiencing a reoccurrence of seborrheic dermatitis. These subjects may have an unscheduled visit (although an unscheduled visit is not required as subjects only need to call the site) when seborrheic dermatitis returns prior to restarting application of investigational product:

- IGA

An updated Body Diagram of seborrheic dermatitis involvement should be provided to the subject.

6.6. Adverse Events

6.6.1. Adverse Event Definition

An AE means any untoward medical occurrence associated with the use of a drug in humans, whether or not considered drug related. An AE can therefore be any unfavorable and unintended sign (including an abnormal laboratory finding), symptom, or disease temporally associated with the use of a medicinal (investigational) product, whether or not related to the medicinal (investigational) product.

AEs will be collected following informed consent of the subject through subject study completion.

A treatment emergent adverse event (TEAE) is defined as an AE that started post application of IP at the Day 1 visit through study completion.

Application site reactions will be considered adverse events if they require intervention, suspension or discontinuation of IP.

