6.6.5. Adverse Event Reporting

The Investigator will review each event and assess its relationship to drug treatment (unrelated, unlikely, possibly, probably, likely). Each sign or symptom reported will be graded on the most current version of the NIH NCI CTCAE toxicity grading scale 5-point severity scale (Grade 1, 2, 3, 4 and 5). The date and time of onset, time relationship to drug dosing, duration, and outcome of each event will be noted.

The relationship of each AE to the IP will be assessed using the following definitions:

Unrelated	
• The AE must clearly be caused by the subject's clinical state, or the study procedure/conditions.• Definitely not related to drug.• Temporal sequence of an AE onset relative to administration of drug not reasonable.• Another obvious cause of an AE.
Unlikely	
• Time sequence is unreasonable.• There is another more likely cause for an AE.
Possibly	
• Corresponds to what is known about the drug.• Time sequence is reasonable.• Could have been due to another equally, likely cause.
Probably	
• Is a known effect of the drug.• Time sequence from taking drug is reasonable.• Ceases on stopping the drug.• Cannot be reasonably explained by the known characteristics of the subject's clinical state.
Likely	
• Is a known effect of the drug (e.g., listed in Physicians' Desk Reference, Compendium of Pharmaceuticals and Specialties, IB).• Time sequence from taking drug is reasonable.• Event stops upon stopping drug, event returns upon restarting drug.

The following CTCAE toxicity grading scale 5-point severity scale definitions for rating maximum severity will be used:

Grade 1	Mild; asymptomatic or mild symptoms; clinical or diagnostic observations only; intervention not indicated.
Grade 2	Moderate; minimal, local or noninvasive intervention indicated; limiting age-appropriate instrumental activities of daily living.*
Grade 3	Severe or medically significant but not immediately life-threatening; Hospitalization or prolongation of hospitalization indicated; disabling; limiting self-care activities of daily living.** Note: An experience may be severe but may not be serious, e.g., severe headache).
Grade 4	Life-threatening consequences; urgent intervention indicated.
Grade 5	Death related to AE.

Note: A semi-colon indicates 'or' within the description of the grade.

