7.2. Safety Evaluation

Descriptive statistics will be calculated for safety data and presented by scheduled study visit for quantitative safety data and frequency counts will be compiled for classification of qualitative safety data. Summaries of local tolerability will be presented by scheduled study visit.

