7.2.1. Adverse Events

All treatment-emergent AEs occurring during the study will be recorded and classified on the basis of MedDRA terminology for the safety population. Treatment-emergent AEs are those AEs with an onset on or after the first date of study treatment in this study. All treatment-emergent AEs will be summarized by treatment group, the number of subjects reporting treatment-emergent AEs, system organ class, preferred term, severity, relationship, and seriousness.

Serious adverse events (SAEs) will be listed by subject. SAEs will be summarized by treatment group, severity, and relationship to study treatment.

For AEs, each subject will be counted only once within a system organ class or a preferred term using the event with the greatest relationship and greatest severity.

All information pertaining to AEs noted during the study will be listed by subject, detailing the verbatim description given by the Investigator, preferred term, system organ class, start date, stop date, severity, action taken regarding IP, corrective treatment, outcome, and drug relatedness. The event onset will also be shown relative (in number of days) to date of first application. In addition, a listing of subjects who prematurely discontinue from the IP due to adverse events will also be provided.

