9.1. Adverse Events

All AEs will be coded using the MedDRA dictionary version 24.1 or above.

A TEAE is defined as an AE that started after application of IP at the Baseline Visit in this extension study. All TEAEs will be summarized from OLE baseline.

An overall summary of TEAEs will be provided; this will present number and percent of subjects who reported at least 1: TEAE (including all TEAEs, TEAEs by maximum severity, and TEAEs by greatest relationship), treatment emergent SAE (TESAE), TEAE leading to study drug withdrawal, TEAE leading to study withdrawal, or TEAE resulting in death.

The number and percent of subjects reporting TEAEs, grouped by MedDRA system organ class (SOC) and preferred term (PT), will be tabulated by all TEAEs, non-serious TEAEs, maximum severity, or greatest relationship to study IP; Cohort and by groups and overall. In the case of multiple occurrences of the same TEAE within the same subject, each subject will only be counted once for each preferred term.

The number and percent of subjects reporting TEAEs will be tabulated by PT and presented by groups and overall.

In the summaries showing severity and relationship to study medication, the event with the maximum severity (mild < moderate < severe) or strongest relationship (not related < related) will be reported. If a particular event is missing the severity and/or relationship, then the strongest possible severity or relationship will be assumed for analysis (severity = severe, relationship = likely).

All the AEs will be listed. The AEs that are treatment emergent will be flagged. Any AEs related to the application site will be flagged in the listing.

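### Local reactions that need no action stay outside the primary TEAE analysis, and the planned tolerability tables cannot show how many subjects ever had one

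*Protocol*

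**What the plan says.** Protocol 6.6.1 starts from a broad definition: "An AE can therefore be any unfavorable and unintended sign (including an abnormal laboratory finding), symptom, or disease". The same section then treats one class of event separately: "Application site reactions will be considered adverse events if they require intervention, suspension or discontinuation of IP". SAP 9.1 builds TEAEs on AEs and adds no rule of its own for local reactions. Occurrence of TEAEs is one of the two primary analyses (Protocol 4.2.1, SAP 2.2.2).

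Local reactions are also scored on two scales (Protocol 6.1.8): an investigator Dermal Response of 0 to 7 with lettered Other Effects, and a subject burning/stinging grade of 0 to 3. Both are taken at Day 1 and at Weeks 4, 12, 24, 36 and 52. On their analysis, Protocol 7.2 says: "Summaries of local tolerability will be presented by scheduled study visit". Protocol 7.2.2 likewise gives counts, percentages and mean or median scores by visit. SAP 9.2 repeats the categorical and continuous summaries and names no per-subject worst or any-time score. Under SAP 6.1.4 an unscheduled or early-termination value enters a visit summary only when the scheduled value is unavailable and the other falls in the window.

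For unscheduled visits, Protocol 6.5 opens its list with "The following information will be collected for all subjects" and names AEs and concomitant medications, with IGA added at recurrence. The tolerability scales are not on the list.

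**The concern.** Local reaction is the most direct harm to look for with a topical product, and long-term safety is the sole objective of this study. The 6.6.1 threshold takes reactions that need no action out of the primary TEAE count. It also thins the mild end of the application-site severity table, because one of the Grade 1 descriptors in Protocol 6.6.5 is that intervention is not indicated: "Mild; asymptomatic or mild symptoms; clinical or diagnostic observations only; intervention not indicated".

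That would matter little if the tolerability tables answered the same question. They do not. A visit-by-visit percentage cannot separate a few subjects with a lasting reaction from many subjects with one brief reaction each. A reader of the study report could not learn how many of about 400 subjects ever reacted locally over a year.

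**Working it through.** The plan gives no figure to reproduce: SAP 3.2 says the sample size rests on no power or precision calculation, and no local-reaction rates are stated.

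**1. Does the sentence restrict?** The general definition in 6.6.1 already covers every local reaction, so the added sentence has work to do only if it narrows. The one score-based trigger for interruption is Dermal Response 5 or greater (Protocol 6.8). Scores 1 to 4 and subject grade 3 have no score-based trigger, so unless the investigator acts on them they can stay outside the AE data.

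**2. Gaps between scored visits.** The schedule days are 1, 29, 85, 169, 253 and 365. The gaps are 29 − 1 = 28, 85 − 29 = 56, 169 − 85 = 84, 253 − 169 = 84 and 365 − 253 = 112 days.

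**3. Chance that a visible reaction is present on a clinic day.** Assume onset is uniform over Days 2 to 364 (363 days), visits fall on the exact day, and the reaction lasts d days (d up to 28). Each of the five visits catches d onset days, less one because Day 365 is outside the onset range: (5d − 1)/363.
- d = 3: 14/363 = 3.9%
- d = 7: 34/363 = 9.4%
- d = 14: 69/363 = 19.0%
- d = 28: 139/363 = 38.3%

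**4. Subject score.** Footnote f of the schedule (Protocol 1.3, repeated in SAP Table 1) limits recall to the application on the day before the visit. Protocol 6.1.8 asks about the time since the last study visit. Under the footnote, five assessments cover 5/364 = 1.4% of treatment days (6/364 = 1.6% with Day 1). Under 6.1.8 they cover every interval, with recall of up to 112 days.

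**5. By-visit count against ever-affected count.** Assume a proportion p with a non-zero score at each of five visits, and N = 400.
- Per visit: 400 × 0.03 = 12; 400 × 0.05 = 20.
- Same subjects every time: 12 or 20 ever affected.
- Independent visits: 400 × (1 − 0.97⁵) = 400 × 0.141, about 57; 400 × (1 − 0.95⁵) = 400 × 0.226, about 90.

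The by-visit table looks the same in both cases.

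**6. Effect on overall TEAE incidence.** Assume q = 1% to 10% of subjects have only sub-threshold local reactions, independent of other TEAEs at an assumed 30% to 50%. The subjects missed number 400 × q × (1 − other TEAE rate): from 400 × 0.01 × 0.5 = 2 to 400 × 0.10 × 0.7 = 28, or 0.5 to 7 percentage points.

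**The case against.** The best defence is that this is separate capture, not omission. Protocol 4.2.1 names Berger and Bowman application-site assessments within the safety endpoint, two dedicated scales record the reactions, and Protocol 6.1.8 gives a reason for care: local reactions must be told apart from pre-existing disease inflammation. That stands. The reactions present at visits are missing from the TEAE analysis, not from the trial.

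Several stronger readings are tempting and are not supported:

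- A reader might infer that the threshold contradicts Protocol 7.2.1, which says "All treatment-emergent AEs occurring during the study will be recorded and classified". It does not. Section 7.2.1 takes AEs as 6.6.1 defines them; the tension is inside 6.6.1.
- A reader might infer that a Grade 1 application-site TEAE is impossible. Protocol 6.6.5 states that semicolons in the grade descriptions mean alternatives, so a reaction with mild symptoms that was treated, or that led to suspension, can be a Grade 1 AE. The tier is reduced, not eliminated.
- SAP 9.1 says "Any AEs related to the application site will be flagged in the listing", which might suggest that such events appear only in listings. Those that qualify as AEs already enter the TEAE tables by system organ class and preferred term, severity and relationship.
- A reader might infer 16 weeks without safety contact. That is the gap between clinic visits at Weeks 36 and 52. The phone visit at Week 44 reviews AEs, so the longest scheduled gap between contacts is 8 weeks. Phone visits do not collect the tolerability scales, however.
- The list in Protocol 6.5 does not forbid scoring at an unscheduled visit. Protocol 6.1 allows additional safety assessments at the investigator's discretion.

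On between-visit burning and stinging, the answer depends on which recall period applies. Visible signs that resolve before a visit can go unscored under either text.

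**Conclusion.** The point holds as a reporting gap that is cheap to close. Local reactions below the 6.6.1 threshold are outside the primary TEAE analysis, and the by-visit tolerability tables do not show how many subjects were ever affected. SAP 8.2.1 plans exactly that any-time view, unscheduled visits included, for IGA outcomes. The plan therefore gives it for benefit but not for local harm.

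The size is not known from the documents. The 57 to 90 subjects should not be read as an estimate: they rest on an assumed 3% to 5% per visit, on independence between visits in the same subject, and on about 400 subjects attending all five visits. Treatment is for up to 52 weeks, and SAP 7.6 refers to subjects who finished before Amendment 1, which added the Week 36 and Week 52 visits, so fewer will attend all five. The count also does not separate new reactions from scores present at baseline. The 2 to 28 subjects for overall TEAE incidence are likewise built on assumed rates.

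**What to change.** - **SAP 9.2:** add a per-subject table of the worst post-baseline Dermal Response, Other Effects and subject burning/stinging score, using any scheduled, unscheduled or early-termination assessment in this study, with the number and percent of subjects ever above baseline. Other Effects are lettered categories, so state the rule, for example any effect not recorded at baseline. The Day 1 subject score is taken after application, so also show the number ever non-zero. Place the table beside the TEAE tables.
- **SAP 9.1:** footnote the TEAE tables with the Protocol 6.6.1 threshold.
- **Protocol 1.3 footnote f, SAP Table 1 footnote f and Protocol 6.1.8:** reconcile the two recall periods, because they decide how much between-visit burning and stinging the new table covers.

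The cost is one extra table from data already collected, a footnote and a wording correction. The reported local-reaction rate will look less favourable. Removing the 6.6.1 threshold is not recommended here: it is a trade-off that could reduce comparability with any parent study that used the same rule, and the table gives the missing information without it.
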